Study Procedure	
 1) Pre-screening by clinical staff per SOP220 to identify potential subjects who would likely meet the criteria for participation in the study. 2) Recruitment Flier is provided electronically and/or hard copy is mailed out with trial Obi Gen3 Medical Robot with triadic recruitment strategy (Provider, Caregiver, Patient) 3) Screening: In-office assessment performed by provider to determine eligibility for home/community trial per Standard Operating Procedures (SOP220) that would be completed regardless of whether participating in the study. While this is not specific to the study procedure, it has been included here to help clarify the process. 4) Informed consent will be obtained for all stakeholders interested in participating (Provider, Caregiver, Patient) electronically using Qualtrics 5) ~ One (1) week home/community trial of Obi Gen 3 with a minimum of a five (5) meal requirement for use by Caregivers and

	
Patients. Providers must recommend and assess at least one (1) patient for Obi Gen 3 in their practice setting.
 
6) Following the ~ one (1) week trial, Qualtrics will send an electronic web-based link.
 
7) Participants who complete the surveys will receive a \$25 electronic gift card
 
8) Optional: Follow-up interviews completed by telephone, if warranted, within one (1) month of survey completion.

Schedule of Events	
1) Pre-Screening
 
2) Recruitment, electronic and paper flyers
 
3) Screening (In-office assessment)
 
4) Informed Consent
 
5) ~One Week Obi Gen3 trial
 
6) Survey completion
 
7) Provide \$25 remuneration
 
8) Optional follow-up interviews

A.2. Identification and description of the Investigational Device

[figure not shown]
[figure not shown]
a) Summary Description of Investigational Device

Obi is a reusable robotic utensil intended to compensate for the function of a human arm during mealtime activities to restore a person's functional eating (self-feeding) status. Obi alleviates/ameliorates the disability caused by medical diseases/conditions that completely or severely impair the upper extremities/limbs. Obi provides a cross-cultural, broad user demographic with the ability to make decisions on what and when to eat through an easy-to-learn and use user interface.

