feeding for individuals with upper extremity impairments—a key activity of daily living that contributes to personal dignity, autonomy, and quality of life.

The claims for clinical performance and effectiveness to be verified in this study include:

- The device can be safely and effectively operated by the intended users (patients and caregivers) in a home, school, or community setting.
- The device is recommended and integrated into practice by clinical professionals who support individuals with feeding-related disabilities.
- The design features, controls, and user interface support efficient, effective, and satisfactory use.
- The device enables users to independently complete a minimum of five meals during a one-week trial period without undue burden on caregivers or providers.

This clinical investigation also aims to verify that supporting materials (e.g., Quick Start Guide, Instructions for Use, and MDNA form) are usable and that the overall user experience aligns with expectations for performance, ease of use, and satisfaction. These claims will be evaluated through mixed-methods data collection, including surveys and semi-structured interviews. No safety claims are being assessed in this study. Obi Gen 3 is a Class I medical device with minimal risk and has undergone benefit-risk analysis and mitigation per ISO 14971. However, participants will be monitored for device-related issues or unanticipated problems during the trial.

b) Objectives, primary and secondary, are described as ‘superiority,’ ‘non-inferiority,’ or ‘equivalence,’ if applicable.

PRIMARY: Validate whether the production equivalent enhanced Obi3 device design conforms to the formally defined user needs and intended use (per IFD-DES-054-1, Obi Validation Plan, Gen3)

SECONDARY:

- Determine patient usability in accordance with the Matching Person & Technology Assistive Technology Framework.
- Determine caregiver usability in accordance with questions from the Caregiver Burden Index.
- Determine provider perspectives following the SUS as a standardized outcome measure.
- Obtain provider feedback regarding the efficacy, efficiency, and satisfaction of the Obi clinical assessment forms and the associated process.
- Obtain other qualitative feedback regarding the perceived strengths and weaknesses of the Obi design.

c) Scientific justification and clinical relevance for effect sizes, non-inferiority margins, or equivalence limits, where applicable.

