This clinical investigation is a non-randomized, non-comparative usability study designed to evaluate whether the Obi Gen 3 Medical Robotic Feeding Device conforms to its intended use and meets documented user needs. The purpose of the study is not to assess therapeutic effectiveness or to compare outcomes across intervention groups but to validate device usability and stakeholder satisfaction across real-world settings.

Given the nature and objectives of the study, randomization, blinding, and allocation concealment are not applicable. However, several measures will be taken to minimize or avoid bias and manage potential confounding factors:

1. Standardized Protocols and Training

All participants (providers, caregivers, and patients) will engage with the device under a standardized study protocol, including consistent onboarding materials, instructional documents, and usage expectations (e.g., a minimum of five meals during the trial period). These materials were developed based on prior formative feedback and are provided in uniform formats to reduce variability in participant experience.

2. Structured Data Collection Tools

Usability feedback will be collected using validated instruments (e.g., System Usability Scale, Matching Person & Technology framework) and semi-structured interview guides. These tools ensure consistency in gathering information, reduce interviewer bias and facilitate comparisons across stakeholder groups.

3. Triangulation of Stakeholder Perspectives

The study design allows for triangulation of findings by including data from three distinct stakeholder groups (providers, caregivers, and patients). This multi-perspective approach reduces the risk of single-source bias and provides a broader understanding of device usability in real-world contexts.

4. Post-Use Feedback After Trial Exposure

Participants provide their usability ratings and feedback only after completing the one-week trial. This approach helps minimize expectation bias and ensures responses reflect the user experience with the device.

5. Blinding of Data Analysts (if applicable)

The Principal Investigator will conduct the data analysis but will not be involved directly in participant recruitment or data collection, reducing the potential for confirmation bias during the interpretation of results.

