Collectively, these measures are designed to support the credibility, reproducibility, and transparency of findings from this usability-focused clinical investigation.

c) Primary and secondary endpoints, with rationale for their selection and measurement. If applicable, composite endpoints, with rationale for their selection and measurement.

Primary Endpoint

The primary endpoint of this clinical investigation is to determine whether the production equivalent Obi Gen 3 device fulfills its intended use and formally defined user needs across three key stakeholder groups: patients, caregivers, and providers. This endpoint reflects the device's design validation objective under FDA and ISO guidelines for Class I medical devices.

To assess this endpoint, the study uses a mixed-methods approach that includes:

- Usability survey responses gathered post-trial via Qualtrics,
- Qualitative interview data to capture real-world experiences and
- Evidence of independent feeding success (i.e., completion of a minimum of five meals during the one-week trial period for patient participants).

Rationale: This endpoint aligns with ISO 13485 and FDA QSR requirements for verifying that a device conforms to documented design inputs and intended use in its target environment. Given that the device facilitates daily living activities rather than delivers clinical treatment, usability, and stakeholder satisfaction are the most relevant performance indicators.

Secondary Endpoints

Secondary endpoints are designed to provide a multi-dimensional understanding of the user experience and support future design refinement and stakeholder-specific training materials.

These include:

1. **Patient Usability** will be measured using an adapted version of the Matching Person & Technology (MPT) Framework and adult and pediatric versions. The study focuses on compatibility between the user and device, perceived benefits, and likelihood of long-term adoption.
2. **Caregiver Usability** will be measured using the System Usability Scale (SUS) and the Matching Person & Technology (MPT) Framework, an adult version adapted for the context of this study. Additionally, a few selective questions from the Caregiver Burden index will help to describe this stakeholder group to understand better the impact of Obi-Gen 3 use on time demands, emotional strain, and caregiving workload.

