3. **Provider perspectives and Workflow Integration** will be measured using the System Usability Scale (SUS) and open-ended feedback. The study will assess ease of device recommendation, assessment form clarity, and integration into the service delivery process.
4. **Effectiveness of Training and Support Materials** will be assessed via post-trial feedback on the Quick Start Guide, Instructions for Use, and clinical assessment documentation (Obi MDNA©).

Rationale: These endpoints reflect stakeholder-specific criteria for acceptability, feasibility, and usability and were selected based on established frameworks in the assistive technology literature.

d) Methods and timing for assessing, recording, and analyzing variables.

This clinical investigation employs a mixed-methods approach to assess the usability and user experience of the Obi Gen 3 Medical Robotic Feeding Device. Both quantitative and qualitative variables will be assessed at multiple timepoints using standardized and non-standardized tools. Data will be recorded electronically and analyzed using descriptive and thematic methods.

Key variables to be assessed include:

- **Usability metrics** (efficiency, effectiveness, satisfaction)
- **Stakeholder-specific experience and acceptance** (patients, caregivers, providers)
- **Functional outcomes** related to self-feeding independence
- **Psychosocial impact** (confidence, autonomy, perceived burden)
- **Feedback on supporting materials** (ease of use of training guides, forms)

As previously described, these variables will be measured using quantitative surveys and rating scales, including the System Usability Scale (SUS) and Matching Person & Technology (MPT) Framework.

Qualitative data will be gathered through open-ended questions, which are included in the surveys, and semi-structured interviews conducted by phone, when applicable.

Timing of Assessments

- **Baseline:** Screening and in-office assessment by providers; completion of the Obi MDNA© form to gather demographics and baseline functional feeding status.
- **During trial:** One-week trial of Obi-Gen 3 in home, community, or school settings. Caregivers and patients use the device with at least five meals; providers recommend or assess at least one user in their practice.

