- **Post-trial (~ one week to one month):** Qualtrics survey links will be sent to all participants (providers, caregivers, patients) to gather information post-trial. Optional telephone interviews may be completed within one month of survey completion for additional qualitative feedback.

Data Recording

- All survey and rating scale responses will be collected electronically via Qualtrics, a HIPAA-compliant data management platform.
- Qualitative interview notes or transcripts will be recorded and stored securely using encrypted formats, with identifiers removed before analysis.

Data Analysis: All analyses will be used to determine whether the design of Obi Gen 3 meets the intended use and user needs and to guide product refinement and support resources.

- Quantitative data will be analyzed using descriptive statistics (e.g., means, standard deviations, medians) to assess trends in usability scores across stakeholder groups.
- As a validated instrument, responses to the SUS will be interpreted using established scoring thresholds to determine whether usability targets were met.
- Qualitative data will be analyzed using a structured thematic coding approach to identify key usability themes, barriers, and suggested improvements.

e) Equipment to be used for assessing the clinical investigation variables and arrangements for monitoring maintenance and calibration.

The primary “equipment” under investigation is the Obi Gen 3 unit, which will be used by patients and caregivers in home, school, or community environments and recommended or assessed by providers in clinical settings. Each Obi Gen 3 unit used in the investigation is a production equivalent model that has

undergone quality assurance testing prior to distribution. DESIN LLC, the device sponsor, is responsible for:

- Verifying proper function of all device components (arm, base, controls) before shipment
- Maintaining a device log to track serial numbers, shipment history, and user assignment
- Providing pre-use visual inspection guidance and basic maintenance instructions to participants.

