- Documentation of any protocol deviations, adverse events, or device-related issues;
- Completion of final data monitoring activities and closure of the Qualtrics data collection system;
- Submission of a final study report following applicable IRB and sponsor requirements.

A.6.2. Investigational Devices and comparators

a) Description of the exposure to the investigational device(s) or comparator(s), if used.

This clinical investigation involves exposure to a single investigational device, the Obi Gen 3 Medical Robotic Feeding Device, which is a production equivalent version of a Class I FDA-registered medical device intended to assist individuals with upper extremity impairments in self-feeding. Participants in the study—including patients, caregivers, and providers—will be exposed to the device during a short-term, observational usability trial, which occurs under real-world use conditions (home, school, community, or clinical environments). No comparator device is being used.

All exposure to the device is consistent with its intended purpose and involves no modification to existing standards of care or risk to participants. The exposure is limited in duration and is conducted in naturalistic settings to allow the device to be evaluated under realistic use conditions.

Patient and Caregiver Exposure: Patients and caregivers will use the Obi Gen 3 device for a period of approximately one week. During the trial, users are expected to operate the device for a minimum of five meals, though additional use is encouraged to gather meaningful feedback. Participants will use the device independently or with caregiver assistance, following a brief orientation via a Quick Start Guide (QSG) and Instructions for Use (IFU) provided with the device. Device use is non-invasive and involves no physical contact beyond standard utensil-based feeding.

Provider Exposure: Providers (e.g. occupational therapists, speech-language pathologists, assistive technology professionals) will interact with the Obi Gen 3 device in the context of:

- Assessing its fit for at least one patient in their caseload,
- Recommending its use as part of routine practice (if applicable),
- and Providing feedback based on observation or guided use in their clinical setting.

The Providers will not operate the device for feeding themselves but will assess functionality, usability, and alignment with therapeutic goals.

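### The independent-feeding evidence for the primary endpoint is defined only as five completed meals, which is also the minimum-use expectation, so by itself it cannot show that meals were completed independently

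*Protocol*

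**What the plan says.** **The claim.** Section A.5 a) lists among the claims to be verified: "The device enables users to independently complete a minimum of five meals during a one-week trial period without undue burden" on caregivers or providers.

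**The measure.** Section A.6.1 c) gives three sources of evidence for the primary endpoint: usability surveys, qualitative interviews, and "Evidence of independent feeding success (i.e., completion of a minimum of five meals during the one-week trial period for patient participants"). The words in the bracket are the only definition given.

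**The use expectation.** The same five meals appear as minimum use in eight places:
- the A.1.5 synopsis, Study Procedure step 5 ("with a minimum of a five (5) meal requirement")
- A.6.1 b) item 1 ("usage expectations (e.g., a minimum of five meals during the trial period")
- A.6.1 d), under the trial period
- A.6.2 a) ("users are expected to operate the device for a minimum of five meals")
- A.6.3 g)
- A.6.4 d), under mitigation of risks
- A.6.4 e)
- A.7 f), where it is set per patient/caregiver dyad and justified as exposure to get past the learning curve

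Section A.7 b) lists the number of meals completed among the participation metrics.

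**Assistance.** A.6.2 a) allows use of the device either independently or with help from a caregiver. The patient inclusion criterion in A.6.3 a) allows participation on the same two footings. Neither says what kind of help is meant.

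**Who is counted.** A.6.1 c) names no denominator for this item. A.6.3 c) i) withdraws patients who turn out on first use, typically on day one, to be unable to use the device safely or effectively. A.7 a) analyses those who complete consent and the survey, and excludes those who leave before completing any trial procedure.

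**The concern.** The word independent stands in the claim and in the label of the measure, but not in the definition of the measure. What remains is a count that coincides with the instruction given to every participant. A report of independent feeding success on this definition would describe adherence to the trial's use expectation. A reader would take it as evidence that patients fed themselves.

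Two things are at stake. The item is named evidence for the primary endpoint, and A.17 commits the sponsor to registering primary endpoints and publishing results, so the label will travel further than its definition. Also, A.7 f) says there are no time-stamped use logs. If participants are not asked how much help was given, no device log can supply it afterwards.

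**Working it through.** The protocol states no figure to reproduce here, and the check involves no power or sample-size arithmetic. It is a comparison of definitions.

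**Step 1. Claim against measure.** A.5 a) needs two things of a patient: at least five meals in the week, and that these were completed independently. A.6.1 c) needs only the first. The measure is therefore necessary for the claim but not sufficient.

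**Step 2. Measure against use expectation.** The threshold in A.6.1 c) (five meals, one week) is the same as the threshold for minimum use in the eight places listed above. A patient who meets the use expectation meets the measure, and one who falls short fails it. The measure thus separates patients by adherence and by nothing else.

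**Step 3. Whether the missing part can vary.** If assisted use were ruled out, the count could stand in for independence. It is not ruled out: A.6.2 a) and A.6.3 a) both allow it. The possible cases are:

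| Patient | A.6.1 c) item | A.5 a) claim |
|---|---|---|
| Five or more meals, all independent | met | met |
| Five or more meals, fewer than five of them independent | met | not met |
| Fewer than five meals | not met | not met |
| Withdrawn on first use as unable to use the device | not met if counted; absent if only remaining patients are counted | not met |

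The second row is the defect: the item and the claim disagree, and the item gives the favourable answer. How many patients fall there is unknown. The protocol does not define an independently completed meal, gives no expected rate of assistance, and does not list assistance per meal among the data summarised in A.7 b).

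**Step 4. Denominator.** The fourth row shows why the population matters. Under A.7 a) a patient withdrawn on first use enters the analysis only if the survey is completed. The protocol does not say whether such patients receive it. A proportion over survey completers may therefore omit the clearest failures; a proportion over all who start the home trial would include them. The protocol gives no rate of first-use failure, so the difference cannot be sized. The anticipated drop-out below 10% in A.7 e) 6) is an expectation for drop-out in general and does not bound it.

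**The case against.** The strongest reply is that little turns on this item. The A.7 g) verdict rests on a one-level fall in the ICF Functional Eating qualifier in 85% of patients, on the absence of serious device effects or health threats, and on user-need responses. The meal count is not among these criteria. This stands, and it limits the weight of the point.

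A second reply is that independence is examined elsewhere. A.5 a) says the claims will be evaluated by surveys and interviews, A.6.1 d) lists functional outcomes on self-feeding independence, and A.6.4 a) has the MDNA form completed again at follow-up. The instruments are not shown and may already ask about help. This also stands. A reader might infer that the study collects nothing on independence, or that its primary conclusion fails; the documents support neither. These sources would not change the definition in A.6.1 c), however, and a one-level fall in the ICF qualifier does not itself show five independently completed meals.

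Third, a reader might infer that the item yields 100% whatever happens. It does so only among patients who meet the use expectation. Most passages call five meals an expectation, and patients can fall short.

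Fourth, a reader might infer that caregivers could do the feeding and still produce a success. The text does not say that. A.6.2 a) expects users to operate the device, and the help allowed may be no more than set-up. The fair statement is that the kind of help is left open, and that this openness is part of the defect.

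Finally, a denominator can ordinarily be left to a statistical analysis plan. Its absence from A.6.1 c) would not be a finding alone. It is raised because the item has to be redefined anyway and A.6.3 c) i) removes a known kind of failure.

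**Conclusion.** The point holds in a limited form. The item in A.6.1 c) carries the label of independent feeding but measures completion of the minimum use asked of everyone. Taken alone it shows exposure and cannot support the A.5 a) claim. It affects one of three listed sources of evidence for the primary endpoint and does not touch the pass/fail rule. Its numerical size cannot be derived from the protocol, and no percentage is offered.

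The conclusion rests on reading the bracketed definition in A.6.1 c) as complete, as its wording presents it, and on the allowance for caregiver help in A.6.2 a) and A.6.3 a). It does not depend on what the unseen surveys or the MDNA form contain; these bear only on how much of the remedy is already in place. The definition should be corrected before the post-trial survey is sent out.

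**What to change.** 1. Reconcile A.5 a), A.6.1 c), A.6.2 a) and A.6.3 a). The sponsor should state what counts as an independently completed meal, and in particular how set-up help and help during feeding are treated. The protocol does not settle this, and no choice is proposed here.
2. Redefine the A.6.1 c) item as at least five independently completed meals in the one-week trial, on that definition.
3. Keep the number of meals completed as a separate participation metric, as in A.7 b).
4. Add one post-trial survey item on the number of meals completed with and without caregiver help during feeding, unless the survey already asks this.
5. Report the proportion reaching the redefined item over all patients who start the home trial, counting those withdrawn for first-use failure under A.6.3 c) i) as not reaching it. Give the figure for the A.7 a) survey-completer population beside it.

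The cost is a few reworded sentences and at most one added survey item. With no use logs, the answer will rest on recall at the end of the week, which is a real weakness and should be acknowledged in the report. The reported figure may be less favourable than the plain meal count.
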